7.4 Storage

All study drugs should be kept in a secure place under appropriate storage conditions. The IP label on the vial/bottle specifies the appropriate storage.

AZD9150 and MEDI4736 are to be stored at the study centre in a secured facility with limited access and controlled temperature (2°C to 8°C). The temperature should be monitored on daily

basis and documented in the temperature monitoring log according to the study drug handling instructions.

AZD5069 (capsules and tablets) is to be stored at the study centre in ambient temperature in a secured facility with limited access. The temperature should be monitored on a daily basis and documented in the temperature monitoring log according to the study drug handling instructions.

Tremelimumab is to be stored with investigational site pharmacy at 2°C to 8°C (36°F to 46°F). Do not freeze.

The IPs must be kept in the original outer container and under conditions specified on the labels.

In the following cases, the centre staff should not use affected study drug and should immediately contact AstraZeneca representative for further guidance:

- Temperature excursion upon receipt or during storage at the study
- Damaged kit upon receipt
- Damaged vial/bottle

Damaged study drug should be documented according to the instructions provided by AstraZeneca representative.

7.5 Distribution of AZD5069 to the patient

A description of how AZD5069 will be packaged for distribution to the patient and detailed instructions how to dispense AZD5069 to the patient will be provided in writing to the study centres before or at the time of site initiation.

7.6 Treatment compliance and accountability

The study drug provided for this study will be used only as directed in the CSP.

The study site staff will account for all study drugs received at the centre, for unused study drugs, and for appropriate destruction (according to local procedures). Certificates of delivery, destruction, and/or return should be signed.

The administration of all medications (including study drug) and details of treatment with IP should be recorded in the appropriate sections of the eCRF.

AZD9150, tremelimumab, and MEDI4736 will be administered IV at the study centre on treatment visits and within visit windows as specified in Section 5.2, [Table 5](#).

AZD5069 will be administered orally by patients at times at the study centre but more often at home as specified in Section 5.2, Table 5. Self-administration of AZD5069 will be recorded in the Patient Diary, which will be used as a measure of compliance. Patients will be asked to return all unused medication and empty containers to the study centre on each treatment visit. The patient's compliance will be assessed by the Investigator and recorded in the eCRF. A capsule/tablet count should be performed at the patient level and recorded in the eCRF as well as in a dispensing log by the study centre personnel.

7.7 Dose-escalation and safety cohorts: Part A and Part B

In the dose-escalation part of the study, 31 evaluable patients were enrolled. At the time of protocol amendment 5, the MTDs/RP2D for each of the 2 agents in combination with MEDI4736 (durvalumab) had been identified [AstraZeneca 2016 (a), AstraZeneca 2016 (b)]. Based upon the safety data gathered from 6 evaluable patients enrolled in Arm A3, the SRC determined on 29 March 2017, that the 80 mg BID alternate dosing schedule for AZD5069 was also a safe and tolerable dose.

All cohorts of Part A will enroll patients with advanced solid malignancies refractory to standard therapy or for which no standard of care regimen currently exists. Following enrolment, based on the patient's history of taking any drugs, herbal supplements, and/or foods prohibited with concurrent administration of AZD5069 or within 14 days of the first dose of AZD5069 and detailed in Section 3.8.2, as well as the patient's anticipated need or likelihood to consume such products at any time throughout the study, the Investigator will then assess whether the patient may be allocated to treatment with AZD5069.

Patients thus excluded by the Investigator from treatment with AZD5069 will be allocated to:

- Treatment arm A4 or A6: AZD9150 in combination with MEDI4736 (AZD9150/MEDI4736/tremelimumab or AZD9150/MEDI4736).

Patients thus included by the Investigator for treatment with AZD5069 will be allocated sequentially to 1 of the following 2 treatment arms:

- Treatment arm A4 or A6: AZD9150 in combination with MEDI4736 (AZD9150/MEDI4736/tremelimumab or AZD9150/MEDI4736), or
- Treatment arm A3: AZD5069 in combination with MEDI4736.

7.7.1 Starting dose and dose-escalation scheme

The starting doses and additional dose levels chosen for each agent in this study were based on the clinical experience with each agent as monotherapy in previous trials.

In Arm A1, AZD9150 was administered at a starting dose of 2 mg/kg IBW. Additional dose level up to 3 mg/kg IBW was evaluated and determined as RP2D. Lower dose selection is

based on PD (STAT3 protein expression) analysis of peripheral blood and tumor biopsy specimens from patients with DLBCL treated in a ISIS Phase 1/2 clinical trial (Clinical study ISIS 481464-CS1, see Section 1.2). The upper limit of 3 mg/kg IBW is based on MTD determination for patients in the same study.

In Arm 2, AZD5069 was administered at a starting dose of 40 mg PO BID (i.e., daily dose of 80 mg). Additional dose level up to 80 mg BID (for a maximum total daily dose of 160 mg) was evaluated. The 40 mg BID dose was considered as the MTD based on initial safety assessment, but based on maturing safety data it was better understood that the DLTs of neutropenia occurring in patients treated with AZD5069 are due to mechanism of AZD5069 (myelokathexis) and are hence functional. The SRC determined to enroll an additional cohort at 80 mg BID dose of AZD5069 with a different dose schedule involving drug holds to manage treatment-related functional toxicities (Arm A3 as described below). The outcome of this cohort has been determined and it concludes 80 mg BID alternate dosing schedule as a viable RP2D. The lowest dose is based on PD (CD11b expression) analysis of peripheral blood cells from healthy volunteers treated in a single ascending dose Phase 1 study (D3550C00001). Arm A3: 6 patients will be initially dosed. If tolerating the dosing schedule well, an additional 6 patients will be added to confirm the dose schedule. If ≥ 2 patients do not tolerate the dose (i.e., meet DLT criteria), the dose will be reduced back to 40 mg BID of AZD5069 (Figure 7 and Figure 8). Non-evaluable patients may be replaced.

For Arm A4, the aim is to conduct a safety run-in of the established dose of AZD9150 (from Arms A1, A2/A3) in combination with a fixed dose of MEDI4736/ tremelimumab in all solid tumor patients. No dose-escalation is planned for Arm A4. If the dose is not tolerated (i.e., patient meets DLT criteria) in this combination of 3 drugs, then dose-reductions will be conducted as described in Figure 4, Figure 7, and Figure 8.

For Arm A6, the dose and safety confirmation cohort, AZD9150 will be given at the established dose of AZD9150 (from Arms A1, A2/A3) in combination with fixed dose of MEDI4736. This will be done in patients with prostate cancer, and there is no intent to do any intra-patient dose escalation. If the dose is not tolerated in this combination of 2 drugs, then dose-reduction will be conducted as in Figure 4, Figure 7, and Figure 8.

MEDI4736 was administered at a dose of 20 mg/kg Q4W.

Tremelimumab was administered at a dose of 1 mg/kg Q4W.

For the definition of DLT, see Section 7.7.3.

In Arms A1 and A2, dose-escalation for the 2 combination treatments (i.e., AZD9150/MEDI4736 and AZD5069/MEDI4736) advanced independent of each other. In addition to determining DLT in the DLT Evaluation period, the SRC critically reviewed all

[figure not shown]
available data pertaining to safety, tolerability, and IM as well as PK, pharmacodynamic, and anti-tumor activity before deciding on the next dose levels/schedules to be explored. Dose-escalation in each arm was considered completed once 1 of the following criteria was met:

- The MTD (for definition of MTD see Section 7.7.4) for the 2 agents in combination have been identified
- The SRC has recommended doses for the 2 agents in combination to be further explored in the dose-expansion Part B
- The maximum doses of the 2 agents in combination have been reached (i.e., AZD9150 3 mg/kg IBW, AZD5069 120 mg BID [for a maximum total daily dose of 240 mg], and MEDI4736 20 mg/kg)

See Figure 4 for the possible dose combinations for study Arms A1, A4, A6 and dose-reduction levels for Part B, and Figure 5 for the possible dose combinations for study Arm A2 and dose-reduction levels for Part B. All potential dose-escalation and de-escalation levels after the starting doses will be determined by the SRC in light of emerging safety, tolerability, and/or PK data (see Section 7.7.6).

[figure not shown]
There will be no intra-patient dose escalations.

Figure 4 Dose-escalation and de-escalation Arms A1, A4, A6 and dose-reduction levels for Part B (B1, B3, B5, and B7)

[figure not shown]
Additional dose combinations not listed in the table may be explored based on emerging safety, tolerability, and/or PK data. All dose combinations will be determined by the SRC. For Part B, AZD9150 will be administered at 3 mg/kg QW.

Figure 5 Dose-escalation and de-escalation Arm A2 and dose-reductions levels for Part B (B2, B4, and B6)

Additional dose combinations not listed in the table may be explored based on emerging safety, tolerability, and/or pharmacokinetic data. All dose combinations will be determined by the SRC. Figure 7, and Figure 8 provide dosing guidelines for Arms A in Part A and for Arm B2 (post first 20 patients) and Arm B4 (post-interim analysis) in Part B. For Part B, AZD5069 will be administered at 40 mg BID.

Figure 6 Dose-reduction levels for treatment Arm B8

[figure not shown]
If body weight decreases to less than 30 kg, weight-based MEDI4736 dosing (20 mg/kg Q4W) will be implemented. No other dose-reductions will be permitted for MEDI4736 for B8.

- AZD9150 Dose level -1: 300 mg Q2W
- AZD9150 Dose level -2: 200 mg Q2W

7.7.2 Management of causally related infusion events

[figure not shown]
For events deemed causally related to infusion of MEDI4736 or tremelimumab refer to Annex 1.

Figure 7 Alternative dose schedule, titration and dose-reduction for Arms A3 and B4 (post-interim analysis)

One round of granulocyte-colony stimulating factor will be permitted when dose-reductions are done in the manner prescribed above. If granulocyte-colony stimulating factor is required for second time, the alternative dose schedule and titration as described in Figure 8 will be followed.

Figure 8 Alternative dose schedule, dose titration and dose-reduction for Arms A3 and B4 (post-interim analysis)

7.7.3 Definition of dose-limiting toxicity

The DLT evaluation period will be defined in Part A of the study as the time from the first dose of AZD9150 or AZD5069 to the end of Cycle 1 (i.e., 35 days total) or until a patient experiences a DLT, whichever occurs first.

A DLT is defined as any AE that occurs from the first dose of study treatment up to the end of the DLT evaluation period, that is judged by the Investigator to be drug-related (i.e., unrelated to PD, intercurrent illness, or concomitant medications), and that is assessed as grade 3 or worse according to the NCI CTCAE, with the following exceptions:

- Increases in transaminase levels (serum glutamic oxaloacetic transaminase [SGOT]/AST and serum glutamic-pyruvic transaminase [SGPT]/ALT) are DLT if:
 - SGOT/AST and/or SGPT/ALT increase to $>15 \times$ ULN at any time, and/or
 - SGOT/AST and/or SGPT/ALT increase to $>10 \times$ to $15 \times$ ULN over a span of 14 consecutive days, and/or
 - SGOT/AST and/or SGPT/ALT increase to $>ULN$, and 1 or more of the following conditions is met and not explained by other causes:
 - (a) TBL increased to $>2 \times$ ULN
 - (b) New appearance of eosinophilia ($>5\%$)
 - (c) Clinical signs of functional liver impairment
- Nausea, vomiting, and diarrhoea will be considered a DLT only if assessed as grade 3 or worse after optimal prophylactic or treatment measures have been prescribed.
- Fatigue will not be considered a DLT.
- Neutropenia will be considered a DLT only:
 - If in the context of grade 3 febrile neutropenia (i.e., absolute neutrophil count [ANC] $<1,000 \text{ mm}^3$ with a single temperature of more than 38.3°C (101°F) or a sustained temperature of at least 38°C (100.4°F) for more than 1 hour;
 - If in the context of grade 4 febrile neutropenia (i.e., ANC $<1,000 \text{ mm}^3$ with life-threatening consequences that indicate urgent intervention);
 - If assessed as grade 3 or worse (i.e., ANC $<1,000 \text{ mm}^3$) and associated with an infection that is clinically severe, associated with sepsis or requiring hospitalization. Grade 3 non febrile neutropenia with clinically minor (as judged by the Investigator) infection need not be regarded as DLT; or
 - If assessed as grade 4 (i.e., ANC $<500 \text{ mm}^3$) for more than 5 days.

- Thrombocytopenia will be considered a DLT only:
 - If assessed as grade 3 or worse (i.e., platelet count $<50,000 \text{ mm}^3$) and associated with bleeding, or
 - If assessed as grade 4 i.e., platelet count $<25,000 \text{ mm}^3$).

Any other grade 3 or grade 4 laboratory evaluations that are asymptomatic will be considered a DLT only if assessed by the Investigator as clinically significant.

Any toxicity judged by the Investigator to be drug-related (i.e., causality rated as possible or greater) that requires study treatment to be discontinued for more than 10 consecutive days will be considered a DLT.

7.7.4 Definition of maximum tolerated dose

A dose will be considered non-tolerated and dose-escalation will cease if $\geq 33\%$ of patients on that dose experience a DLT. Once the non-tolerated dose is defined, the MTD will be confirmed at a dose level below the non-tolerated dose or a dose between the non-tolerated dose and the last tolerated dose may be investigated. At least 6 evaluable patients are required to determine the MTD.

7.7.5 Definition of dose-limiting toxicity evaluable patient

For patients in treatment arms A1 and A4 (AZD9150/MEDI4736 or AZD9150/MEDI4736/tremelimumab), to be deemed evaluable for dose-escalation purposes, a patient must have received all 3 loading doses of AZD9150 during the 7-day lead-in period and at least 3 additional doses during Cycle 1 as well as the MEDI4736 and tremelimumab infusion during the DLT Evaluation period or have suffered a DLT within the first 35 days of treatment.

For patients in treatment arm A2 or A3 (AZD5069/MEDI4736 or AZD5069/MEDI4736/tremelimumab), to be deemed evaluable for dose-escalation purposes, a patient must have received all doses during the 7-day lead-in period (i.e., 14 doses) and at least 42 additional doses of AZD5069 or 50% of planned doses during the DLT Evaluation period) as well as the MEDI4736 infusion and remained active on trial at the end of Day 35 of the study.

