For Arm A6: the dose and safety confirmation cohort AZD9150 will be given in combination with MEDI4736 at established doses of AZD9150 (from Arms A1, A2/A3) in combination with a fixed dose of MEDI4736. This will be done in patients with prostate cancer and there will be no intra-patient dose escalation. If the dose is not tolerated in this combination of 2 drugs, then dose-reduction will be conducted as shown in [Figure 4](#), [Figure 7](#), and [Figure 8](#).

Potential subjects who provide written informed consent will be screened; those who are identified as eligible will be enrolled, assessed by the Investigator for treatment with AZD5069, and assigned accordingly to a treatment arm. Following a 7-day lead-in period during which only AZD9150 or AZD5069 will be administered, combination treatment with MEDI4736 and/or tremelimumab starts on Day 1 of Cycle 1. A cycle of study treatment is defined as 28 days.

Each patient will undergo assessments for safety (DLTs, AEs, vital sign measurements, clinical laboratory tests, PS, ECGs, and physical examinations) and other assessments according to the study plan (see [Section 5.2](#)).

The DLT evaluation period will be defined as the time from the first dose of AZD9150 or AZD5069 to the end of Cycle 1 (i.e., 35 days total), or until a patient experiences a DLT, whichever occurs first. For patients in treatment arm A4 (AZD9150/MEDI4736/tremelimumab), to be deemed evaluable, a patient must have received all 3 loading doses of AZD9150 during the 7-day lead-in period, and at least 3 additional doses during Cycle 1, as well as the MEDI4736 and tremelimumab infusion during the DLT evaluation period. Patients who have suffered a DLT during or before Day 35 will also be deemed evaluable. For patients in treatment arm A3 (AZD5069/MEDI4736) to be deemed evaluable, they must have received all doses during the 7-day lead-in period (i.e., 14 doses) and at least 50% of the planned doses of AZD5069.

For Arm A6, the aim is to establish, collect, and confirm safety, tolerability, and PK/pharmacodynamic relations of the RP2D/MT2D for the 2 combinations (i.e., AZD9150/MEDI4736 and AZD5069/MEDI4736) in specific tumor types of prostate cancer at established doses from Arms A1, A2, and A3. Hence, Arm A6 will not be followed for DLTs.

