## Statistical Analysis Plan

### 6.2. KEY DEFINITIONS

For the purposes of this study, the term “study drug” is restricted to AZD9056, AZD9150, MEDI4736, treme, and the 4 drug combinations, AZD9056/MEDI4736, AZD9150/MEDI4736, AZD9056/MEDI4736/treme and AZD9150/MEDI4736/treme.

Study Day is the day relative to the date of the first dose of study drug in Cycle 1. If a date falls on or after the date of the first dose in Cycle 1, then the corresponding Study Day is calculated as (Study date) – (Date of first dose in Cycle 1) + 1. If a date falls before the date of first dose in Cycle 1, the corresponding Study Day is calculated as (Study date) – (Date of first dose in Cycle 1). Day -1 is the day immediately before the date of the first dose in Cycle 1.

The last dose date is defined as the last non-missing date where a non-zero dose of study drug was recorded. For patients who are ongoing at the time of an interim analysis, the last dose date will be considered the date of the most recent study visit in the database for that patient where a non-zero dose of study drug was recorded.

Unless otherwise specified, baseline is the last non-missing observation before the start of study treatment in Cycle 1.

In treatment arm A1 (AZD9150/MEDI4736), A4 (AZD9150/MEDI4736 or AZD9150/MEDI4736/treme) in dose escalation Part A, an evaluable patient must have received all 3 loading doses of AZD9150 during the 7-day Lead-in period and at least 3 additional doses during Cycle 1 as well as the MEDI4736 and treme infusion during the DLT Evaluation period or have suffered a DLT within the first 35 days of treatment. In treatment arm A2 (AZD5069/MEDI4736) in dose escalation Part A, an evaluable patient must have received all doses during the 7-day Lead-in period (i.e., 14 doses) and at least 42 additional doses as well as the MEDI4736 infusion during the DLT Evaluation period or have suffered a DLT during or before the first 35 days of treatment.

An efficacy evaluable patient is defined as a patient with unidimensional measurable disease at baseline as per the RECIST version 1.1 criteria who received at least 1 dose of study treatment.

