### 11.1.3. Confirmation of the Presumed Recommended Dose

Once the MTDs for each of the 2 agents in combination with MEDI4736 have been identified or the maximum doses of each of the 2 agents in combination with MEDI4736 have been reached, the SRC may decide to enrol an additional cohort of at least 6 evaluable patients per treatment arm to confirm the presumed recommended dose for each of the 2 agents in combination with MEDI4736 to be further explored in the dose-expansion Part B.

Once all patients have completed Part A, the final estimates of the proportion of DLTs for each tested dose-level of the 2 combination will be summarized.

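### Protocol 7.7.5 gives arms A2/A3 no DLT route to evaluability, in conflict with Protocol 4.1.2 and SAP 6.2; arm A3 is left without an unambiguous exception, and the dose minimum differs between the three places.

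*Protocol*

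**What the plan says.** Protocol 7.7.5 defines evaluability for two pairs of arms. For A1 and A4 a patient qualifies either through dosing or through the event itself: the rule ends "infusion during the DLT Evaluation period or have suffered a DLT within the first 35 days of treatment". For A2 and A3 it asks for all 14 lead-in doses, then 42 further AZD5069 doses or half of those planned, "as well as the MEDI4736 infusion and remained active on trial at the end of Day 35 of the study". No DLT alternative follows.

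Two other places deal with the same matter.

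- Protocol 4.1.2 states "Patients who have suffered a DLT during or before Day 35 will also be deemed evaluable". The sentence comes directly after the A4 rule and before the A3 rule. The A3 rule asks for the lead-in doses "and at least 50% of the planned doses of AZD5069" and has no DLT clause of its own.
- SAP 6.2 gives A2 the lead-in doses, "at least 42 additional doses as well as the MEDI4736 infusion during the DLT Evaluation period", and then the alternative "or have suffered a DLT during or before the first 35 days of treatment". It has no rule for A3.

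Evaluability feeds several Part A outputs. The MTD, a primary safety endpoint, rests on patients who completed the DLT evaluation (SAP 4.5.1). The CRM playbook uses evaluable patients only (SAP 11.1.2). At the end of Part A, "the final estimates of the proportion of DLTs for each tested dose-level of the 2 combination will be summarized" (SAP 11.1.3), with no denominator named. SAP Table 3, by contrast, puts DLTs on the Safety set.

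**The concern.** A DLT-evaluable set normally admits a patient by adequate exposure without an event, or by the event. If the second route is missing, the patients whose toxicity took them off the trial are the ones removed, and the DLT proportion falls. The A2/A3 paragraph of 7.7.5 omits that route and adds a Day 35 condition that appears nowhere else.

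The unequal dose minima add to the problem. Under Protocol 7.7.3, a drug-related toxicity "that requires study treatment to be discontinued for more than 10 consecutive days will be considered a DLT". Whether a patient with that kind of DLT passes the dose test depends on which passage is applied. A Part A primary safety result would then rest on a set that two people could build differently from the same documents.

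**Working it through.** **1. The rules side by side**

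| Place | Arm | Minimum after lead-in | Active at Day 35 | DLT alternative |
|---|---|---|---|---|
| Protocol 7.7.5 | A1, A4 | 3 AZD9150 doses | not required | yes |
| Protocol 7.7.5 | A2, A3 | 42 doses or 50% of planned | required | none |
| Protocol 4.1.2 | A4 | 3 AZD9150 doses | not required | yes, next sentence |
| Protocol 4.1.2 | A3 | 50% of planned | not required | only if the preceding sentence is read as general |
| SAP 6.2 | A1, A4 | 3 AZD9150 doses | not required | yes |
| SAP 6.2 | A2 | 42 doses | not required | yes |
| SAP 6.2 | A3 | no rule | no rule | no rule |

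A2 has an explicit exception in the SAP. A3 has none that is free of doubt.

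**2. Dose arithmetic**

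- Lead-in: 7 days × 2 = 14 doses, which reproduces the protocol's figure.
- Cycle 1: 28 days × 2 = 56 doses. Whole 35-day period: 14 + 56 = 70.
- 42/56 = 75%, which allows (56 − 42)/2 = 7 missed days in Cycle 1.
- 50% of 56 = 28, which allows 14 missed days. If the half is taken over all 70 doses it is 35, or 21 beyond the lead-in.
- The shortest hold that counts as a DLT on duration is 11 days. Within Cycle 1 it leaves at most 56 − 22 = 34 doses, which is below 42 and above 28 (and above 21).

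**3. Direction of the effect**

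Take d DLTs in n patients and exclude e of the DLT patients. The proportion changes from d/n to (d − e)/(n − e). The fall is e(n − d)/[n(n − e)], which is positive whenever d < n. If the excluded patients are replaced by patients without a DLT, it becomes (d − e)/n, which is lower still. The literal rule can therefore only understate the proportion.

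**4. Possible size, under an assumption**

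Let p be the true DLT rate and q the share of DLT patients excluded and replaced. The rate among evaluable patients is p(1 − q)/(1 − pq). The documents give no value for q, so a range is shown for p = 0.33.

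| q | Rate among evaluable patients | P(at least 2 DLTs in 6) |
|---|---|---|
| 0 | 0.33 | 0.642 |
| 0.25 | 0.27 | 0.512 |
| 0.5 | 0.198 | 0.339 |
| 0.75 | 0.11 | 0.134 |
| 1 | 0 | 0 |

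This shows what the literal text would do if it governed the count. It is not an estimate for this trial.

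**5. Which definition the SAP uses**

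SAP 11.1.2 points to the protocol's Section 6.2, but Protocol 6.2 defines serious adverse events. SAP 11.1.1 points to protocol Section 5.4.3, which is the ECG section. SAP 13 declares no change to DLT evaluability. The references do not settle which text governs.

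**The case against.** The case that this is only a drafting matter is strong on several points.

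- The sentence in Protocol 4.1.2 is worded for patients in general, and SAP 6.2 states the exception outright for A2. A reader might infer that A2/A3 patients with a DLT have no exception anywhere. That is wrong for A2 and open to argument for A3.
- A reader might infer that a DLT defined by a long hold disqualifies its own patient under 7.7.5. It does not on dose grounds for a hold within Cycle 1, because 7.7.5 accepts 42 doses or 50%, and 34 exceeds 28. It fails only the 42-dose rule in SAP 6.2, where the A2 exception applies. A patient off drug is also not necessarily off the trial, since Protocol 3.9.1 separates the two.
- A reader might infer that the A3 rate was understated. Protocol 4.1.2 reports one DLT among the 6 patients first assessed, and Protocol 7.7 says the Safety Review Committee relied on 6 evaluable patients. Read together, the DLT was counted.
- The A3 decision rule in Protocol 7.7.1 is a count of at least 2 patients meeting DLT criteria. Protocol 7.7.4 refers to patients on the dose and needs at least 6 evaluable patients for the MTD. The committee reviews all available safety data. Non-evaluable patients may be replaced (Protocol 7.7.1) or will be (SAP 11.1.1).
- The two minima may have been meant per arm, with 50% for A3 because it has scheduled holds.
- All Part A arms are closed, so no dosing decision can change.

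All of this stands, and it limits the point to an inconsistency. It does not remove it: 7.7.5 still says what it says for A3, does not say that its minima are arm-specific, and SAP 11.1.3 still lacks a denominator. The Safety set in SAP Table 3 keeps every DLT, but it also includes dosed patients who left early without one, so it is a different proportion from the one based on evaluable patients.

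**Conclusion.** The point holds as a conflict between Protocol 7.7.5, Protocol 4.1.2 and SAP 6.2. It is clearest for A3, where no passage gives the DLT exception without doubt. Applied as written, 7.7.5 would exclude A2/A3 patients who left because of a DLT and would bias the DLT proportion downwards. No such exclusion is shown, and the reported A3 result of 1 in 6 (16.7%) appears to include its DLT, so no bias in this trial is demonstrated.

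The dose minima of 75% and 50% of Cycle 1 are not equivalent, and an 11-day hold falls between them. The calculation in terms of q rests on an assumed share of excluded patients, on their replacement, and on a count restricted to evaluable patients. It indicates possible scale only. The matter is worth correcting because the MTD endpoint and the CRM data depend on evaluability and the final DLT proportions have no stated denominator.

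**What to change.** 1. In the A2/A3 paragraph of Protocol 7.7.5, add the DLT alternative already used there for A1/A4 and in SAP 6.2 for A2. The same paragraph describes A2/A3 as possibly including tremelimumab, which conflicts with the A3 description elsewhere and should be reconciled.
2. Add an A3 definition with that clause to SAP 6.2, and correct the section references in SAP 11.1.1 and 11.1.2.
3. Reconcile the dose minimum for each arm across Protocol 7.7.5, Protocol 4.1.2 and SAP 6.2. Which minimum applies to which arm is for the sponsor to state.
4. In SAP 11.1.3, name a denominator that includes every patient with a DLT, and say how it relates to the Safety set in SAP Table 3.

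The cost is a sentence or two in each document and a re-check of the few A2/A3 patients who had a DLT or left before Day 35. No new data are needed.
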